#### 1.0 Background

Exploring and eating food is one of the most critical occupations for children. However, some children experience challenges impacting their ability to interact with food in a healthy way. Feeding challenges can negatively impact a child's quality of life and health (Cunliffe et al., 2022).

There are many reasons that children do not eat the variety and amount of foods required for optimum health. Some children have structural, neurological, or medical challenges impacting their ability to tolerate foods (Kamarudin et al., 2023). For optimal outcomes, these areas must be addressed and treated. However, following treatment, sometimes difficulty accepting food remains.

#### **Food Avoidance**

Food avoidance can occur within nonclinical and clinical populations (Cunliffe et al., 2022; Chao, 2018). Diagnoses or terms used to describe children who have challenges eating a variety of foods and trying new foods include picky eaters, children with food neophobia, and avoidant/restrictive food intake disorder (ARFID). A child presents with picky eating (PE) when they eat a limited variety of foods, have rigidity around the sensory qualities of food, and demonstrate difficulty trying new foods (Barnhart et al., 2021). PE is not a medically defined term but describes restrictive food intake behavior common among children (Chao, 2018).

Taylor and Emmett (2019) discuss the prevalence of PE among toddlers and state that food-related behavior in infants under 12 months should not be considered PE or neophobia due to their lack of experience with food. Cardona Cano et al. (2015) completed a study including 4,018 participants examining the trajectory of PE in childhood. At age 1.5 years, 26.5% of children were reported to have PE behavior, and at age 3, parents reported a slight increase to

27.6%. However, at age 6, only 13.2% of children had reported PE behavior. The authors cautiously speculated that PE behaviors at age 6 suggest risk factors for worse health outcomes than children without a history of PE. While transient PE may be part of typical development in the toddler and preschool years, persistent and severe PE will likely lead to poor health outcomes. It is estimated that PE is common and ranges from 25% to 53%, with statistics differing by country (Kamarudin et al., 2023).

Food neophobia relates to the fear and avoidance of novel foods and can relate to visual attention bias toward the food (Maiz & Balluerka, 2018). Hazley et al. (2022) completed a study and found that food neophobia peaked at approximately age 6. The prevalence of food neophobia is not widely understood due to no universal way of measuring and defining food neophobia (Białek-Dratwa et al., 2022).

According to the Diagnostic and Statistical Manual of Mental Disorders 5th edition (2022), the diagnosis of ARFID captures a wide variety of feeding disturbances and leads to inference with psychosocial functioning and failure to meet nutritional and energy needs. Dinkler et al. (2022) found that children at risk for ARFID began to demonstrate more food-avoidant behaviors than their peers during toddlerhood. Sanchez Cerezo et al. (2022) completed a systematic review to understand the epidemiology of ARFID. They found that most studies reported a prevalence rate between 5%-22.5%. Anxiety disorders were found to be common within the population of children and adolescents diagnosed with ARFID studied, ranging from 9.1%-72%.

## **Impact of Feeding and Eating Challenges**

Anxiety surrounding food can be debilitating for a child. Difficulties tolerating a variety of foods due to anxiety can negatively impact many areas of a child's life, including nutrition,

energy, self-esteem, self-regulation, and social interactions (Maiz & Balluerka, 2018).

Selfregulation's definition can vary based on the theoretical framework as noted within cognitive learning and sensory integration theories (Martini et al., 2016). Kuypers (2013) defined selfregulation as obtaining and maintaining an optimal level of alertness to function. Kuypers also included the ability to manage emotions and sensory needs to participate in occupations such as schoolwork and activities of daily living as part of self-regulation.

Shree and Murthy (2021) completed a study and concluded that there is a significant association between scholastic performance and nutritional status. Zickgraf and Elkins (2018) discussed how PE is problematic from both a psychosocial and nutritional standpoint. Maiz & Balluerka (2018) found that children with food neophobia scored lower on the social and family dimensions of self-concept than their peers.

In addition, parents of children who experience anxiety surrounding food report increased stress (Cunliffe et al., 2022). Zickgraf and Elkins (2018) stated that parents of children with PE experience anxiety, stress, and family conflict. Kim et al. (2021) completed a study examining parent strategies for expanding food variety and perceptions of helpfulness as reported by adults with symptoms of ARFID. The study found that while strategies to increase the pleasure of the eating experience could make a positive change, forceful strategies were not perceived as helpful.

Children's feeding difficulties and food avoidance are significant concerns for parents and healthcare providers. Food avoidance can impact a child's growth, physical well-being, and health later in life (Zickgraf & Elkins, 2018). Grey et al. (2021) completed a systematic review to understand the effects of famine and food restriction on children as they grew to adulthood. They

found a consistent association between significant childhood malnutrition with adult increased risk for cardiovascular disease, metabolic syndrome, and hypertension. While children with food avoidance behavior do not have forced food restrictions, such as children experiencing a famine, malnutrition due to poor intake of vegetables and proteins limits their nutritional health and micronutrient intake (Kamarudin et al., 2023). In addition, Padhani et al. (2022) discussed how malnutrition can contribute to a weakened immune system.

#### **Anxiety and Picky Eating**

Anxiety appears to contribute to challenges with food tolerance for children with food neophobia, ARFID and PE. Zickgraf and Elkins (2018) completed a study to understand the relationship between anxiety, sensory sensitivity, and PE. They found that children who had identified anxiety demonstrated increased sensitivity to sensory input. Increased sensory sensitivity is predictive of PE behavior. The researchers linked anxiety to both state and trait sensory sensitivity. It is unclear, per the study completed by Zickgraf and Elkins, if anxiety causes sensory sensitivity. Therefore, best practice requires the treatment of both anxiety and sensory sensitivity.

Most research supports the concept that children with food avoidance also have anxiety and challenges with regulation. Maiz and Balluerka (2018) found that children with food neophobia scored higher on trait anxiety. State anxiety refers to a natural anxiety response to danger. This type of anxiety is experienced only when danger is present and is not related to an underlying anxiety condition. Trait anxiety describes someone who experiences anxiety most of the time as part of their personality, not only when presented with a trigger. Santos et al. (2022) completed a study suggesting that children's emotion regulation predicted healthy food consumption. These studies support the hypothesis that treatment for children who are picky

eaters supporting regulation and decreasing anxiety would improve healthy eating habits.

IronSegev et al. (2020) generated research that showed more emotional disturbances occur in children with ARFID compared to the control group. In contrast, this study showed no significant difference between the control group and the group with an ARFID diagnosis on anxiety outcome measures.

#### **Researched Interventions**

Interventions that have been proven effective in helping children with neophobia tolerate foods include cognitive behavioral therapy, routine following, food exposure, sensory play, and tactile food exploration (Kamarudin et al., 2023; Thomas et al., 2020; Merritt & Caldwell, 2020; Garcia et al., 2020; Nekitsing et al., 2019; Karagiannaki et al., 2021). Beyond sensory play, limited recent studies exist regarding sensory strategies to calm during feeding. One article contained a randomized controlled trial and studied the use of mindful breathing techniques and mindful eating when trying new food. This study found that children ages 10-12 years old who used mindfulness techniques increased their intake of novel fruit but did not decrease their anxiety or food neophobia, as shown by outcome measures of the Food Situations Questionnaire and Spence Children's Anxiety Scale Teddy Picture Rating Scale (Bennett et al., 2020). However, this was the only article on this subject, and it had many limitations, including a small number of participants. Using breathing techniques to calm children with food neophobia appears to lack research and warrants future study.

#### Weighted Blankets

Weighted blankets have increased in availability and popularity in recent years. A systematic review study found that weighted blankets reduce anxiety (Eron et al., 2020).

Occupational therapy practitioners (OTP) use deep pressure techniques such as weighted

blankets during treatment to improve a client's ability to self-regulate and calm. A study including functional magnetic resonance imaging and a compression sleeve to provide deep pressure without human touch completed by Case et al. (2021) found that deep pressure was calming to the nervous system. Reynolds et al. (2015) completed a study examining deep pressure applied with an inflatable vest and found that participants who were stressed by a challenge experienced a decreased arousal level following the deep pressure. Lane et al. (2012) had previously completed a study that positively correlated anxiety in children ages 6-10 years with sympathetic measures of arousal level. Lönn et al. (2023) found weighted blankets to improve sleep efficiency in children diagnosed with attention-deficit/hyperactivity disorder with a mean age of 9 years using a randomized controlled crossover trial. The children reported increased satisfaction with the weighted blanket compared to the control blanket. Meth et al. (2022) found that melatonin was secreted in young adults when provided with a weighted blanket at bedtime. Vinson et al. (2020) found that anxiety was reduced in people receiving chemotherapy who used a weighted blanket. Dickson et al. (2021) completed a small study where the participants in a psychiatric ward reported decreased anger and anxiety in their posttest scores. Becklund et al. (2021) produced a study that showed statistically significant decreases in anxiety in adults at an inpatient psychiatric facility who utilized a weighted blanket. Bolic Baric et al. (2021) examined the effectiveness of weighted blanket use on sleep and activities of daily living among participants with diagnoses of autism spectrum disorder and attention deficit hyperactivity disorder. They found that weighted blankets improved sleep at night and relaxation during the day. These studies further support the use of deep pressure as a treatment strategy for calming and regulation. Improved self-regulation can allow for improved participation in occupations such as eating.

While no studies were found supporting the use of weighted blankets with children with anxiety-related food avoidance, the findings from the pilot randomized controlled trial completed by Ohene et al. (2022) found that weighted blankets combined with traditional occupational therapy (OT) may benefit adults diagnosed with anorexia nervosa and AFRID. The use of weighted blankets to calm children who experience food avoidance appears to be an area requiring study.

#### 2.0 Rationale and Specific Aims

#### **Contribution to Occupational Therapy**

Many children experience anxiety-related food avoidance, and there is a dearth of research on sensory strategies to address these difficulties. Researchers must explore intervention options to provide individualized and appropriate care for children with eating challenges related to anxiety. The fourth edition of the *Occupational Therapy Practice Framework: Domain and Process* describes well-being, health, and occupational engagement as central concepts of OT (American Occupational Therapy Association [AOTA], 2020). AOTA (2017) clarifies the role of the OTP within the occupation of eating, including providing environmental modifications. My aim for my capstone is to produce scholarly work and research to support these core OT values in pediatric feeding and expand on environmental modification treatment options. While Ohene et al. (2022) completed a pilot study examining the sensory strategy of weighted blankets with adults with ARFD and anorexia nervosa, no research has been published to understand if weighted blankets might be helpful for children with feeding issues. Completing research in pediatric food avoidance and treatment strategies provides additional evidence-based treatment options for OTPs to help children within this population.

AOTA (2016) describes the importance of scholarship and creating new knowledge to contribute to the profession and society. Boyer (1990) describes the *scholarship of discovery* as a disciplined and structured investigation to gain understanding. I intend to research this topic without bias to provide novel information using a studied treatment strategy in an innovative way, thus participating in the scholarship of discovery. Furthermore, the OT *Standards for Continuing Competence* generated by AOTA (2015) demands that OTPs use evidence-based knowledge and critical reasoning skills to provide best-practice therapy. Therefore, the profession of OT must continue to provide cutting-edge research and add to the body of existing knowledge.

#### **Proposed Pilot Study**

This small experimental pilot study addresses the knowledge gap related to the use of weighted blankets for children with anxiety related to food and eating. My plan includes recruiting a minimum of seven children who receive OT treatment at the clinic where I work and clinics in the surrounding area. However, I would like permission to recruit twelve children due to concerns with attrition. The design of the study will include a control period prior to the treatment period. This study will seek to understand if children improve their ability to self regulate and calm with the use of a weighted blanket when trying new foods. It will also attempt to research whether children improve novel food consumption using a weighted blanket.

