#### 5.0 Study Procedures

- 1. Recruitment
- 2. Consent
- 3. Enrollment of participants based on inclusion and exclusion criteria.
- 4. Guardians of enrolled participants will complete the baseline outcome measure

  Food Neophobia Scale for Children (FNSC) questionnaire consisting of 10 questions

  (Pliner, 1994). Guardians of participants will also complete an initial food list on the
  initial food log form including all foods that the participant currently tolerates. Included
  on the initial food log form will be a place for the caregiver to record the age and weight
  of the child. The weight of the child will be used to calculate the appropriate weight of
  the weighted blanket. The weighted blanket will not exceed 10% of the child's body
  weight. Weighted blankets are commercially available through the company yescool for
  children in weights of ten pounds, seven pounds, five pounds, and three pounds. Each
  participant will receive a weighted blanket that is approximately 10% of their body

weight but does not exceed 10% of their body weight. For example, if a child weighs 55 pounds, they will receive a five-pound weighted blanket. The initial food log form including the initial food list and weight of the child will be scanned and returned to the caregiver prior to the control period. The FNSC will be collected.

- 5. Participants will receive occupational therapy services treatment as usual without use of a weighted blanket for 1 month. During this period, participants will complete the S-Anxiety scale of the State-Trait Anxiety Inventory for Children (STAIC) three times per week upon sitting at the table prior to a meal (Spielberger, 1973). The S-Anxiety scale questionnaire will take about 8-12 minutes for a child to complete the first time and 5-8 minutes for repeated administrations. All forms and scales necessary for the control period will be provided to the caregivers prior to the control period of the study.
- 6. After the 1-month control period, caregivers will complete the FNSC and complete the second food list adding any new foods to the initial food log (Pliner, 1994). The principal investigator will collect the FNSC and the initial food log form at this time.

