- 7. Following the 1-month control period, participants and their guardians will receive a weighted blanket with verbal and written instructions for use and safety. The participants will continue usual care occupational therapy treatment during the treatment period. The caregivers will be provided with copies of the S-Anxiety scale of the STAIC, new food log, and a copy of the initial food log for reference (Spielberger, 1973). Participants will be instructed to use the weighted blanket for at least 5 minutes and no more than 15 minutes while participating in a quiet enjoyable activity prior to a meal with guardian supervision. Guardians will be responsible to keep the weighted blanket when not in use. Due to busy family schedules, it may not be possible to use

the blanket daily, therefore, the family will be asked to offer use of the blanket a minimum of 3 meals a week. On the days that the weighted blanket was used, the participant will complete the S-Anxiety scale of the STAIC at the table where they will consume the meal, following using the blanket and before eating the food (Spielberger, 1973). The guardians will be asked to record any new foods tried during the meal on the new food log along with the date each time the participant uses the weighted blanket.

- Upon completion of the 1-month treatment period, the guardians will complete the FNSC (Pliner, 1994). The principal investigator will collect the FNSC, new food log, and S-Anxiety scale of the STAIC at this time either through HIPAA protected email or in-person (Spielberger, 1973).
- 10. Once the study is completed the guardians will be gifted the weighted blanket to use as they deem appropriate

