#### **6.0 Study Product Description**

A weighted blanket 10% or less of the participant's body weight will be used under parent or therapist supervision as a calming strategy prior to introduction to new food paired with a preferred stationary task such as watching a video or reading a book.

Weighted blankets are commercially available for children in weights of ten pounds, seven pounds, five pounds, and three pounds through the company yescool (yescool, n.d.). The blankets are made from glass beads and breathable polyester microfiber fabric according to the Amazon website. The glass beads are enclosed in five inch by 5 inch square compartments and stitched by high-density 15000 stitches to secure the glass beads within the blanket. Each participant will receive a weighted blanket that is approximately 10% of their body weight but does not exceed 10% of their body weight. For example, if a child weighs 55 pounds, they will receive a five-pound weighted blanket.

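### S-Anxiety is taken before any meal while the aim concerns new food, and the records as written do not allow the two months to be compared by meal type

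*Combined protocol and SAP*

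**What the plan says.** Section 2.0 (Proposed Pilot Study) asks whether children "improve their ability to self regulate and calm with the use of a weighted blanket when trying new foods". Section 6.0 (Study Product Description) describes the blanket as used "as a calming strategy prior to introduction to new food paired with a preferred stationary task".

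Section 5.0 (Study Procedures) does not carry the new-food condition into the measurements:

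- Control month, step 5: the child completes the S-Anxiety scale "three times per week upon sitting at the table prior to a meal".
- Treatment month, step 7: the blanket is used "while participating in a quiet enjoyable activity prior to a meal with guardian supervision", and "the family will be asked to offer use of the blanket a minimum of 3 meals a week". On timing: "On the days that the weighted blanket was used, the participant will complete the S-Anxiety scale of the STAIC at the table", after the blanket and before eating.

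New foods are recorded differently in the two months. In the control month, caregivers add new foods to the initial list once, at the end (step 6). In the treatment month, guardians log the new foods tried at each blanket meal, with the date (step 7).

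Section 12.0 compares the treatment-month mean S-Anxiety score with the control-month mean by a paired t-test. It does not mention meal type. Section 4.0 states that there is no randomization and that the control month always comes first.

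**The concern.** A family could follow section 5.0 to the letter using familiar meals only. The S-Anxiety result would then describe anxiety before ordinary meals, which is not the question in 2.0.

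The second problem is comparability. Families choose which meals are measured, and nothing in the text keeps the share of new-food meals equal across the two months. If new food raises anxiety, a change in that share moves the period mean whether or not the blanket works. The S-Anxiety scale is completed before eating, so the relevant exposure is what is served, not what is later tried. Foods served and refused are recorded in neither month.

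**Working it through.** The plan gives no figure for this point, so there is nothing to reproduce. The check has three parts.

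**1. What can be classified from the records, by the text**

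| | Control month | Treatment month |
|---|---|---|
| Occasion for S-Anxiety | any meal, 3 per week | any blanket meal, blanket offered at 3 or more meals per week |
| New food required at that meal | not stated | not stated |
| New food tried: date or meal known | no, one list at month end | yes, dated log for blanket meals |
| New food served but refused | not recorded | not recorded |
| S-Anxiety form stated to carry a date | no | no |
| Meal type used in 12.0 | no | no |

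Control-month forms cannot be sorted into new-food and familiar meals. Treatment-month forms can be sorted only in part, and only if the form can be matched to the log. A between-month contrast by meal type is therefore not available.

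**2. Bias from a change in meal mix**

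Let p_C and p_T be the shares of readings at new-food meals in the control and treatment months, D the mean rise in S-Anxiety at a new-food meal, and B the blanket effect (negative means benefit, taken as equal for both meal types).

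- Control mean = familiar-meal mean + p_C x D
- Treatment mean = familiar-meal mean + p_T x D + B
- Difference = B + (p_T - p_C) x D

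The second term is the bias. It is zero if the mix does not change. More forms per child do not remove it.

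D and the shares are not in the documents. The ranges below are assumptions: D of 0.5, 1 or 2 SDs of the paired difference, a shift of 25 or 50 percentage points common to all children, and two-sided alpha 0.05. The sample sizes of 7 and 12 come from 2.0. Probabilities are from the noncentral t distribution.

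With no blanket effect (B = 0), the nominal chance of p<0.05 is 5%:

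| D | Shift (points) | Size of bias (SD) | n = 7 | n = 12 |
|---|---|---|---|---|
| 0.5 | 25 | 0.5 x 0.25 = 0.125 | 6% | 7% |
| 0.5 | 50 | 0.5 x 0.50 = 0.25 | 9% | 12% |
| 1 | 25 | 1 x 0.25 = 0.25 | 9% | 12% |
| 1 | 50 | 1 x 0.50 = 0.50 | 20% | 35% |
| 2 | 25 | 2 x 0.25 = 0.50 | 20% | 35% |
| 2 | 50 | 2 x 0.50 = 1.00 | 60% | 88% |

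A fall in the share looks like a benefit; a rise looks like harm.

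With a true benefit of 1.0 SD (B = -1), power with no mix change is 60% (n = 7) or 88% (n = 12). If the share rises in the treatment month:

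| D | Rise (points) | Remaining difference (SD) | n = 7 | n = 12 |
|---|---|---|---|---|
| 0.5 | 25 | -1 + 0.125 = -0.875 | 49% | 79% |
| 1 | 25 | -1 + 0.25 = -0.75 | 39% | 66% |
| 1 | 50 | -1 + 0.50 = -0.50 | 20% | 35% |
| 2 | 50 | -1 + 1.00 = 0 | 5% | 5% |

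**3. How much data a comparison by meal type would have**

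Taking a month as 4 weeks, 3 x 4 = 12 forms per child per month. A new-food share of 25% gives 12 x 0.25 = 3 forms, and a share of 10% gives 12 x 0.10 = 1.2. If meals are treated as independent, the chance that a child has no new-food form in a month is 0.75^12 = 3% at a 25% share and 0.90^12 = 28% at a 10% share.

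**The case against.** Several counter-arguments have force.

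- **The treatment-month log.** A reader might infer that new-food meals are not identified at all. The text does not support that: blanket meals at which a new food was tried are dated. The gaps are the control month, refused foods in both months, and the absence of a stated link from log to S-Anxiety form.
- **New-food counts.** Section 12.0 already compares the number of new foods between months, so a gross shift would be partly visible. That stands, but the count concerns foods tried, not the share of measured meals at which a new food was served. The count may also rise because the blanket works.
- **The forms are not reproduced.** The caregiver forms and guardian handout are not in the document and may hold more. Only the text can be judged, and it asks for no such item.
- **The aim can be read more broadly.** Section 2.0 also speaks of anxiety about food and eating, and 10.0 of the mealtime experience. Pre-meal state anxiety is a defensible pilot measure of that. Restating the aim would resolve the mismatch with the measurements, though not the change in mix.
- **Analysing new-food meals carries its own bias.** It is tempting to make the new-food-meal contrast the main analysis. The study also asks whether the blanket increases novel food consumption, so serving new food may itself respond to the blanket. Selecting on it can bias the comparison, and some of the 7 to 12 children could have no usable pair. This stands, and it is why that analysis should be supportive only.

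**Conclusion.** The point holds in a limited form. The aim and product description concern new food. The anxiety measurements are tied to any meal and averaged over all readings, and the records as described do not allow the two months to be compared by meal type. A family could comply fully and still produce a result that does not answer the stated question.

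The size of any bias is (p_T - p_C) x D and cannot be derived from the documents. Under the assumed ranges it runs from 0.125 to 1.0 SD of the paired difference, and it is zero if the mix does not change.

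A reader might infer that the design is set to produce a false benefit. The documents do not support that. A new-food log issued with the blanket may encourage more new-food meals in the treatment month, which would hide a benefit; only a fall would mimic one. Meal mix is also one of several uncontrolled differences between months in a fixed-order pilot. This is an inexpensive improvement, not a reason to hold the study.

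**What to change.** 1. On every S-Anxiety form in both months, record the date, the meal, and whether a food not on the child's list is being served (yes/no). This must be in place before the control month, because meal type cannot be reliably reconstructed later.
2. Keep the all-meal paired comparison in 12.0. Report the share of new-food meals by month beside it.
3. Add a supportive comparison of the two months within new-food meals and within familiar meals, and state that serving new food may itself be affected by the blanket.
4. Reconcile the new-food wording in 2.0 and 6.0 (Study Product Description) with the any-meal wording in 5.0.
5. If new-food meals are too few, limit the conclusion to pre-meal anxiety in general.

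The cost is one or two extra items per form beyond the date and a few sentences in 12.0. The drawback is thin data in the supportive comparison: few new-food forms per child, and some children possibly with none in one month.

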#### 12.0 Biostatics and Subsidies

A statistical analysis using IBM SPSS Statistics (Version 28) predictive analytics software will be completed. The STAIC S-Anxiety scale mean score during the treatment period will be compared to the control period mean score using paired-samples t-tests (Spielberger,

1973). The control period mean score will be compared to the baseline. Similarly, the raw score from the FNSC during the treatment period and the raw control period score will be compared using paired-samples t-tests to understand if the children demonstrated a statistically significant change in food neophobia (Pliner, 1994). The control period raw score will be compared to baseline raw score using paired-samples t-tests. Nonparametric analysis will be used as necessary.

The average number of foods tried during the control period will be compared to baseline and the average number of new foods tried during the control period will be compared to the average number of new foods tried in the treatment period to understand if more foods were tried when using the weighted blanket. A paired-sample t-test will be completed to compare the control period to the treatment period. Nonparametric analysis will be used as necessary.

A weighted blanket will be provided to each of the participants of this study for their use following the study at no cost to the participant. The weighted blankets will be purchased by the principal investigator. This study is not funded by grants or subsidies.

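### The second aim is novel food consumption, but the plan counts new foods tried, states no record of swallowing or acceptance, and collects the count differently in the two months

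*Combined protocol and SAP*

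**What the plan says.** - **Aim.** Section 2.0, Proposed Pilot Study: "It will also attempt to research whether children improve novel food consumption using a weighted blanket".
- **Pre-study record.** Section 5.0, step 4, has guardians complete an "initial food log form including all foods that the participant currently tolerates". No list of foods previously tried or refused is mentioned.
- **Control month.** Section 5.0, step 6, has caregivers, at the end of the month, "complete the second food list adding any new foods to the initial food log". This step does not use the word tried and does not say what qualifies a food for the list.
- **Treatment month.** Section 5.0, step 7, gives guardians a "new food log, and a copy of the initial food log for reference". It continues: "The guardians will be asked to record any new foods tried during the meal on the new food log". They also enter the date, and they do this each time the blanket is used.
- **Analysis.** Section 12.0 compares the average number of new foods tried in the two months by a paired t-test, or a nonparametric method as needed, "to understand if more foods were tried when using the weighted blanket". It also compares the foods tried in the control month with baseline.

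No section defines new, tried or consumption, sets a minimum amount, or asks for acceptance.

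**The concern.** Trying a food and consuming it are different outcomes, and the background in section 1.0 treats them as such: it bases the health rationale on poor intake and describes a cited trial's result as intake of a novel fruit. If the count of foods tried rises, a report written to the stated aim could present more tasting as more consumption.

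The word novel has a similar gap. The only pre-study list is of tolerated foods, so a food the child has met and refused before is not on it. Every participant is already in occupational therapy for feeding challenges (section 3.0, inclusion criterion 2), so earlier exposure to foods that are not tolerated is plausible.

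The more consequential risk lies in the comparison between months. If the control-month list captures foods that became tolerated and the treatment-month log captures foods that were tried, the paired difference mixes a change in behaviour with a change in what is recorded.

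**Working it through.** The plan gives no figure for the food endpoint (no expected count, standard deviation or effect size), so there is nothing to reproduce. The check sets the recording rules side by side.

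| | Pre-study | Control month | Treatment month |
|---|---|---|---|
| What is listed | Foods tolerated | New foods, added to the tolerated list | New foods tried |
| When | Once, at baseline | Once, at month end | At each blanket meal, with date |
| Meals covered | Not applicable | No restriction stated | Meals where the blanket is used |
| Swallowed or accepted | Implied by tolerated | Not stated, perhaps implied by the list | Not stated |
| Term in section 12.0 | Baseline | Foods tried | Foods tried |

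**Step 1: consumption.** Under the treatment-month rule, a new food tasted and rejected is still a food tried and adds 1. A new food eaten in full also adds 1. The count described cannot tell them apart.

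**Step 2: novelty.** A food refused before the study is not on the tolerated list. If it is tried in the treatment month, and the guardian takes new to mean not on the reference log, it adds 1. If it is offered and refused again, it adds 0. By then the reference log also holds the control-month additions, so a description of it as tolerated foods only is exact just for the pre-study list.

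**Step 3: comparability of the months.** Take an assumed child who tastes four foods and accepts one in each month.

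- Control month, guardian extends the tolerated list with what was accepted: count = 1.
- Treatment month, guardian logs what was tried: count = 4.
- Recorded difference = 4 − 1 = 3, with no change in behaviour.

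If the guardian instead adds every tasted food in the control month, the difference is 4 − 4 = 0. The recorded result for the same behaviour therefore ranges from 0 to 3, depending on how step 6 is read. A further difference pulls the other way: the treatment log covers blanket meals only, while no such limit is stated for the control month. The net direction cannot be fixed from the documents.

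**Step 4: other sources.** The Food Neophobia Scale is a 10-question caregiver questionnaire and the S-Anxiety scale measures anxiety. Neither is described as recording which foods were eaten. Section 6.0 (Sources of Research Material) rules out the use of records, so therapy notes could not supply earlier refusals under the plan.

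**Step 5: baseline comparison.** Section 12.0 compares foods tried in the control month with baseline, but the baseline list is of foods tolerated. The same mismatch appears there.

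**The case against.** The strongest reply is that this is a matter of undefined words. The aims paragraph itself also speaks of trying new foods, section 12.0 states its own question in terms of foods tried, and the Food Neophobia Scale at three time points gives a second view of the same problem. Each child is their own control, so a loose definition applied equally in both months would give a broader construct rather than a bias towards the blanket.

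Part of this stands. If the recording were the same in both months, the comparison would be a fair one of foods tried, and rewording the aim would be enough. But the two recording rules differ, so equal application cannot be assumed, and even a fair difference in foods tried is not a difference in consumption.

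A reader might infer more than the text supports:

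- *That a rejected bite is scored as a treatment success.* The plan sets no success threshold. The outcome is a count, and counting a rejected bite is the plain reading of tried, not an explicit rule.
- *That a long-refused food counts as soon as it is offered again.* It has to be tried, and the guardian has to read new as not on the list. The log is supplied only for reference, and a guardian could take new to mean never eaten before.
- *That the log form does not ask about swallowing.* The form, the written instructions and the safety handout are not reproduced. Only the silence of the protocol text can be stated.

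**Conclusion.** The mismatch is present in the current text and no other section resolves it: the aim is consumption, the analysed count is foods tried, and the two months are recorded under different rules. Followed as written, the plan could report more tasting, or a change in recording, as more novel food consumption.

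The size cannot be estimated, because the documents give no expected counts and no split between tasted and accepted foods. The range of 0 to 3 foods in the illustration shows the mechanism under assumed behaviour and is not a forecast. The conclusion rests on two readings: that tried includes a taste not swallowed, and that the unseen forms add no acceptance item.

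It would go too far to say that the design is biased in favour of the blanket, since the differences in recording pull in both directions. It would also go too far to say that the food data have no value for the second aim: they bear on willingness to try foods, and modest changes to the forms would let them address consumption.

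**What to change.** 1. Use the same new-food log in both months, filled in at the same kind of meal. The meals at which the S-Anxiety scale is completed are a ready anchor, since that scale is used in both months.
2. Add one tick per food: tasted only, swallowed, or would eat again.
3. In section 12.0, define the consumption endpoint as the number of distinct foods not on the tolerated list that were swallowed at least once. State whether control-month additions update that list for the treatment month. Keep any food tried as a supporting count.
4. Count previously refused foods that are now swallowed. Excluding them would score a plausible benefit as zero in children already in feeding therapy. If guardians can list such foods at baseline, report them as a descriptive split, not an exclusion.
5. If the forms cannot be changed, restate the aim and the conclusion as willingness to try foods not currently tolerated. This aligns the aim with the count but does not make the two months comparable, so the difference in recording should then be reported as a limitation.

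The cost is a little more recording for guardians, mainly in the control month, and a few sentences in sections 5.0 and 12.0. The stricter endpoint will give a smaller count, which matters with 7 to 12 children and is the reason to keep the broader count beside it.
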